#### Sample size justification

Since this is primarily a safety study we based our sample size on the ability to detect changes in our secondary outcomes, especially metabolomics. Previous studies of supplementation of UDCA and TUDCA have resulted in alterations in the total serum bile acid levels (2-8 fold change) and the composition of the bile acid pool. Based on our preliminary data, to detect a 50 - 70% change in levels of an individual bile acid, with a power of 85% and two-tailed alpha of 0.05 the required sample size would be between 14 – 27 in each arm. Accounting for a 10% drop-out rate, we will aim to recruit 30 participants in each arm of the trial. We have previously noted significant alterations in metabolic profiles in MS patients treated with vitamin D and dimethyl fumarate in studies utilizing between 18-24 patients (as shown in preliminary data).

From a safety stand-point, a sample size of 30 would enable us to conclude with 80% confidence that the rate of occurrence of serious adverse events with TUDCA treatment was less than 5% if none of the patients experienced a serious adverse event during the study[40].

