#### **d. Early stopping rules.**

We will discontinue treatment if a participant develops abnormal safety labs (serum AST or ALT > 3 x upper limit of normal, serum bilirubin > 3 x upper limit of normal, eGFR < 60ml/min/1.73m^2), becomes pregnant during the study, cannot tolerate the drug, develops an adverse event grade 3 or higher that is possibly related to study treatment or wants to discontinue treatment. Any death that is at least possibly related to the study will put the study on hold. The Data and Safety Monitoring Board will determine if it is safe to resume the study. Subjects who become suicidal during the study (codes 1-4, <http://www.fda.gov/downloads/Drugs/GuidanceComplianceRegulatoryInformation/Guidance/UCM225130.pdf>) will be referred to a psychiatrist or to a psychiatric emergency room for evaluation at the discretion of the site treating physician.

Data and Safety Monitoring Board (DSMB): An independent DSMB will be utilized for subject monitoring. The DSMB will consist of a neurologist, a hepatologist and a statistician. The DSMB will meet every 12 weeks and any time an SAE occurs. All SAEs will be reported to the DSMB delegates within 24 hours of the study staff becoming aware of the SAE. The DSMB will be required to review SAEs and respond with recommendations within two business days. If more than 3 subjects experience serious adverse events, the study will be put on hold and the DSMB will decide on whether the adverse events were secondary to study treatment. They will make a judgement as to whether the study should continue and, if so, whether a reduction in TUDCA dosing or other protocol modifications are recommended.

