### c. Plan for reporting unanticipated problems or study deviations.

Unexpected Adverse Event: An adverse event is considered unexpected when its nature or severity is not consistent with the product information (e.g. package insert safety information, the investigational plan, the investigator's brochure, the protocol, or the informed consent form).

Serious Adverse Event: A serious adverse event (any adverse event that suggests a significant hazard, contraindication, side effect, or precaution) must be reported. This includes, but may not be limited to, death, a life-threatening event, inpatient hospitalization or prolongation of existing hospitalization, persistent or significant disability/ incapacity, congenital anomaly/ birth defect, other protocol-specified conditions, or an event that requires intervention to prevent permanent impairment or damage. Serious adverse events will be collected from informed consent signing until 30 days after study completion or until 30 days after a participant withdraws from the study.

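### The zero-SAE assurance is slightly optimistic (78.5% rather than 80% confidence), and no bound is planned if one or more TUDCA patients have an SAE

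*Combined protocol and SAP*

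**What the plan says.** Section 7a makes safety and tolerability primary, judged on the number of adverse events in the two groups and drop-out in each arm.

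Under Sample size justification (Section 7c), the authors explain that "we based our sample size on the ability to detect changes in our secondary outcomes, especially metabolomics". The required 14 to 27 per arm is then raised to allow for loss ("Accounting for a 10% drop-out rate"), and the resulting target reads "we will aim to recruit 30 participants in each arm of the trial". A separate paragraph adds the safety statement: "a sample size of 30 would enable us to conclude with 80% confidence that the rate of occurrence of serious adverse events" on TUDCA is below 5%. The claim is limited to one case, namely "if none of the patients experienced a serious adverse event during the study". The method and the sidedness of the 80% are not given there.

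Three other places bear on the point:
- The analysis text of Section 7c summarises adverse events by system organ class, severity and relationship to treatment, and tolerability as a number and percentage. It plans no confidence interval or bound for the SAE proportion and names no safety population.
- Section 7d says: "If more than 3 subjects experience serious adverse events, the study will be put on hold". It also has the DSMB meet whenever an SAE occurs, and a possibly related death triggers a hold of its own.
- Section 8c collects SAEs from consent "until 30 days after study completion or until 30 days after a participant withdraws from the study".

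**The concern.** The safety sentence is the plan's only precision statement about SAEs, and Aim 1 is to establish safety. It raises two questions: whether 30 patients with no SAE deliver the stated confidence, and what the trial can say if the zero-event condition fails.

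The second matters more. Section 7d foresees the trial running on with one, two or three affected subjects, so a finished trial with a non-zero count is an ordinary outcome under the plan. The prepared statement would then not apply and nothing replaces it. A reader who carried away the 5% figure would have a mistaken idea of which SAE rates the trial had excluded, and the form of the safety conclusion would be chosen after the count was known.

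**Working it through.** **Inputs.** From Section 7c: n = 30 TUDCA patients, a rate of 5% to be excluded, 80% confidence, zero SAEs and 10% drop-out. The 80% is read as a one-sided upper bound, since the claim is that the rate lies below a value. The count is of patients with at least one SAE.

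**Step 1: the plan's own figure.** With zero events, the confidence that the rate is below p is 1 − (1 − p)^n.
- n = 30, p = 0.05: 1 − 0.95^30 = 1 − 0.2146 = 78.5%. The plan says 80%.
- 80% upper bound: 1 − 0.20^(1/30) = 5.2%. The plan says below 5%.
- Patients needed for a strict 80%: ln(0.20)/ln(0.95) = 31.4, so 32. These give 80.6% and a bound of 4.9%.
- 95% upper bound for 0/30: 1 − 0.05^(1/30) = 9.5%.

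The stated figure is thus approximately reproduced: 1.5 points and two patients short.

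**Step 2: other methods.** A Poisson approximation needs 1.609/0.05 = 32.2, so 33 patients. A two-sided 80% interval needs ln(0.10)/ln(0.95) = 44.9, so 45. A uniform-prior Bayesian calculation gives 79.6% at n = 30, and a Jeffreys prior gives 92.2%.

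**Step 3: one or more SAEs.** For x affected patients the exact (Clopper-Pearson) one-sided bound is the Beta(x + 1, n − x) quantile at the chosen confidence level. The confidence that the rate is below 5% is 1 − P(X ≤ x | n, 0.05). For x = 1 this is 1 − (0.95^30 + 30 × 0.05 × 0.95^29) = 1 − (0.2146 + 0.3389) = 44.7%, using unrounded terms.

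| Affected among 30 on TUDCA | 80% upper bound | 95% upper bound | Confidence rate is below 5% |
|---|---|---|---|
| 0 | 5.2% | 9.5% | 78.5% |
| 1 | 9.7% | 14.9% | 44.7% |
| 2 | 13.7% | 19.5% | 18.8% |
| 3 | 17.6% | 23.9% | 6.1% |

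**Step 4: how often the zero-event condition would hold.** The documents give no background SAE rate, so these rates are assumptions. At true per-patient risks of 1%, 2%, 3% and 5%, the chance of no SAE in 30, (1 − p)^30, is 74%, 55%, 40% and 21%. The bounds in Step 3 do not depend on these rates.

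**Step 5: the denominator.** Ten per cent drop-out takes 30 to 27. If all three drop-outs were lost to SAE follow-up, zero events in 27 would give 1 − 0.95^27 = 75.0% confidence, with bounds of 1 − 0.20^(1/27) = 5.8% and 1 − 0.05^(1/27) = 10.5%. This is a sensitivity case and not the expected one, because Section 8c keeps collecting SAEs for 30 days after withdrawal.

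**The case against.** The strongest reply is that the sentence uses round numbers, and 78.5% or a bound of 5.2% is what one would expect behind 80% and 5%. That stands. A reader might infer that the plan contains an arithmetic error or that 30 patients fail the safety aim. The documents do not support this: the method is not stated, and some Bayesian versions come very close to 80% or exceed it. On the exact binomial calculation, slightly optimistic is as far as one can go.

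A reader might also infer that drop-out cuts the assurance to 75.0% with a 5.8% bound. The 10% allowance is made for the bile-acid sample size, and Section 8c follows withdrawn patients for SAEs, so all treated patients can stay in the denominator. Section 4f removes participants who develop an SAE, so a completers-only count would exclude the events of interest. What stands is narrower: the plan does not name the denominator, and some patients will have had less than 16 weeks of treatment.

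Third, the sentence is openly conditional on zero events, and SAEs are handled through the DSMB and the hold rule. Both are true, so the missing bounds are an omission and not a false statement. But DSMB review and a hold are monitoring. They do not supply an estimate of the rate when the trial ends.

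Finally, the plan declares its 80% level openly, and nobody is misled into thinking it is 95%. That stands too. Adding the 95% bound is a matter of usefulness, not a correction.

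**Conclusion.** The concern holds as a minor point. For 30 treated patients with no SAE, the claim is marginally overstated: 78.5% against 80% confidence, or 5.2% against 5%. The larger part is that no bound is planned for one or more affected patients, although the trial may continue with up to three. A single affected TUDCA patient raises the 80% bound from 5.2% to 9.7% and the 95% bound from 9.5% to 14.9%.

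This rests on a one-sided exact binomial reading, all 30 TUDCA patients counted, and the SAEs in question falling in that arm; the hold rule counts subjects without naming an arm. A reader might infer that the sample size is undermined. It is not, because it was derived from metabolomics, and neither a test nor the hold rule uses the 80%/5% figure.

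**What to change.** Three additions to Section 7c:

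1. Replace the safety sentence with: with 30 treated and no SAE, the exact one-sided upper bound on the SAE rate is 5.2% at 80% and 9.5% at 95% confidence.
2. State that the denominator is all treated TUDCA patients, counting patients with at least one SAE. If wanted, give 5.8% and 10.5% for 27 as a sensitivity case in which every drop-out is lost to SAE follow-up.
3. State that the exact upper 95% bound will be reported for whatever number of TUDCA patients has an SAE.

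The cost is a few sentences and a slightly less favourable stated figure. No patients, visits or monitoring rules change.

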#### **d. Early stopping rules.**

We will discontinue treatment if a participant develops abnormal safety labs (serum AST or ALT > 3 x upper limit of normal, serum bilirubin > 3 x upper limit of normal, eGFR < 60ml/min/1.73m^2), becomes pregnant during the study, cannot tolerate the drug, develops an adverse event grade 3 or higher that is possibly related to study treatment or wants to discontinue treatment. Any death that is at least possibly related to the study will put the study on hold. The Data and Safety Monitoring Board will determine if it is safe to resume the study. Subjects who become suicidal during the study (codes 1-4, <http://www.fda.gov/downloads/Drugs/GuidanceComplianceRegulatoryInformation/Guidance/UCM225130.pdf>) will be referred to a psychiatrist or to a psychiatric emergency room for evaluation at the discretion of the site treating physician.

Data and Safety Monitoring Board (DSMB): An independent DSMB will be utilized for subject monitoring. The DSMB will consist of a neurologist, a hepatologist and a statistician. The DSMB will meet every 12 weeks and any time an SAE occurs. All SAEs will be reported to the DSMB delegates within 24 hours of the study staff becoming aware of the SAE. The DSMB will be required to review SAEs and respond with recommendations within two business days. If more than 3 subjects experience serious adverse events, the study will be put on hold and the DSMB will decide on whether the adverse events were secondary to study treatment. They will make a judgement as to whether the study should continue and, if so, whether a reduction in TUDCA dosing or other protocol modifications are recommended.

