### **Study visits and procedures:**

Study procedures that can be done remotely will be conducted via video visit to minimize patient contact and provide scheduling flexibility to participants.

1. **Screening visit (-2 weeks)\*\*:** At the screening visit participants will undergo the following procedures.
  - a. Informed consent
  - b. Collection of demographic and disease characteristics
  - c. Collection of concomitant medication information
  - d. Vital signs, physical and neurological examination\*
  - e. Verification of eligibility based on inclusion/ exclusion criteria
  - f. Venipuncture for baseline safety laboratory testing\*
  - g. MSFC\* and MSQOL-54 assessments
  - h. Urine pregnancy test\*
  - i. Suicidality evaluation (C-SSRS)

If the participant is eligible for the trial, they will then return for the baseline visit at which time they will be randomized to a treatment group and begin the trial.

2. **Baseline visit (0 weeks)\*\*:**

Following procedures will occur at this visit:

- a. Screening laboratory tests will be reviewed to assess whether there is any contraindication for continuation in trial
- b. Update concomitant medication information

- c. Update medical and disease history
- d. Vital signs, physical and neurological information\*
- e. Venipuncture for PBMCs and safety laboratory tests\*
- f. Stool specimen collection
- g. MSFC\*, MSQOL-54 and Food frequency questionnaire assessments
- h. EDSS evaluation\*
- i. Urine pregnancy test\*
- j. Suicidality evaluation

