**4. End-of-study visit (16 weeks)**

The following procedures will occur at this study visit.

- a. Assessment of adverse effects
- b. Review of safety labs
- c. Update medical and disease history
- d. Update concomitant medication information
- e. Vital signs, physical and neurological examination\*
- f. Venipuncture for PBMCs and safety labs\*
- g. Stool specimen collection
- h. MSFC\*, MSQOL-54 and Food frequency questionnaire assessments
- i. EDSS evaluation\*
- j. Urine pregnancy test\*
- k. Suicidality evaluation

\*Must be done at in-person portion of visit

\*\* Due to the COVID-19 pandemic and to make it more convenient for the patients to participate, we decided to offer the option of three visits instead of four as an alternative. In this case, we will perform the research blood draw and stool sample at the screening visit, along with providing patients with medicine. We will ask patients not to start taking medicine until we receive the screening lab results and let them know whether they are eligible and can start the medication.

Study procedure	Screening	Baseline Week 0	Week 8	Week 16
Written consent	X			
Verify eligibility	X			
Medical history, relapse assessment	X	X	X	X
Medication review (also antibiotic and probiotic use)	X	X	X	X
Vital signs, physical, neurologic (EDSS) exams*	X	X	X	X
MS Functional Composite* & MSQOL-54	X	X	X	X
Adverse event assessment		X	X	X
Food frequency questionnaire		X	X	X
Laboratory testing (CBC, CMP, HbA1c, Lipid profile, pregnancy test)*	X	X	X	X
Blood for PBMC isolation* & Stool specimen collection		X	X	X
Suicidality evaluation (C-SSRS)	X	X	X	X

\*Must be done at in-person portion of visit

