**f. Definition of treatment failure or participant removal criteria.**

Patients selected for the study will be removed if they:

- 1) They develop abnormal safety labs as defined below
- 2) Develop a serious adverse event
- 3) Inform us that they became pregnant during the study
- 4) Are unable to follow the requirement of the study
- 5) Request to be removed

**g. Description of what happens to participants receiving therapy when study ends or if a participant's participation in the study ends prematurely.**

The subject's medical care will continue unaltered when the study ends or if a subject is removed from the study.

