**5. Inclusion/Exclusion Criteria**

The inclusion and exclusion criteria for participants in this trial are listed in the table below.

Eligibility criterion	Rationale
Diagnosis of Progressive MS based on Lublin criteria	We are focusing on people with PMS since they are more likely to have low bile acid levels
Age ≥ 18 years	To include only adults in the trial
On the same therapy for the past 6 months and not expected to switch therapy in the next 6 months	To avoid confounding by changes in immunomodulatory therapy during the trial
No relapse in the past 3 months	To avoid any confounding introduced by relapse
Exclusion criterion	Rationale
No previous history of liver disease	Confounding due to decreased bile acid production or altered bile acid metabolism
No stage IV/V chronic kidney disease or other severe metabolic derangements	To reduce risk of adverse effects or confounding due to other systemic disorders
BMI < 15 kg/m  and BMI > 40 kg/m 	Reduce confounding due to extremes of BMI
Female patients who are pregnant or nursing, or not	Prevent potential teratogenicity

willing to use contraception	
Chronic antibiotic use	Prevent confounding of microbiome analyses
Corticosteroid treatment within the past 30 days	Prevent confounding of treatment effect
Known history of other neuroinflammatory, neurodegenerative or systemic autoimmune disease	These diseases could require other treatments or be affected by the trial medication.
No current or prior history of the following – 
 
• Bariatric surgery
 
• Small intestinal surgery resulting in loss of length of the jejunum or ileum
 
• Chronic diseases of the small intestine (e.g., Crohn’s Disease, gluten sensitive enteropathy, or other disorders that could lead to malabsorption)
 
• Abnormal bile duct anatomy
 
• Sclerosing cholangitis
 
• Anti-mitochondrial antibodies
 
	These conditions could alter bile acid handling in the gut or bile acid levels in circulation

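### Minor, cheap to fix: entry excludes only stage IV/V kidney disease, but treatment stops at eGFR below 60, so eGFR 30-59 can meet the entry criteria while already beyond the stopping limit

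*Combined protocol and SAP*

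**What the plan says.** **Entry (section 5).** The only renal line in the eligibility table is "No stage IV/V chronic kidney disease or other severe metabolic derangements". It sits under the exclusion heading but is worded as a negative. Read by its evident intent, it keeps out stage IV and V. No eGFR figure appears there.

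**Stopping and removal (sections 7d and 4f).** Treatment is discontinued if a participant *develops* abnormal safety labs, with limits including "serum bilirubin > 3 x upper limit of normal, eGFR < 60ml/min/1.73m"². Section 4f makes the same labs a reason for removal: "They develop abnormal safety labs as defined below". The limit is absolute, and neither section says how to treat someone already below it at entry.

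**Checks before dosing (section 4a).**
- The screening visit includes "Verification of eligibility based on inclusion/ exclusion criteria".
- At the baseline visit, item 2a reads: "Screening laboratory tests will be reviewed to assess whether there is any contraindication for continuation in trial".
- In the three-visit option, staff look at the screening labs and "let them know whether they are eligible and can start the medication".

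None of these states a renal threshold. The schedule lists a CMP at screening, baseline, week 8 and week 16. It is the only listed test that could supply an eGFR.

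**The concern.** A stopping limit should be one that every person admitted by the entry criteria starts on the safe side of. Here the two rules use different scales, a disease stage at entry and an eGFR value on treatment, and they do not meet.

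The checks before dosing could bridge the gap, but they do not clearly do so. The screening check and the three-visit option ask whether the person is eligible, which leads back to criteria with no eGFR figure. Item 2a asks more broadly about contraindications, and a careful physician may apply 60 there, but nothing instructs them to.

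Safety and tolerability are the primary outcome, measured by adverse events and by drop-out in each arm (section 7a). An ambiguous stopping limit therefore touches what the trial is designed to report, and two staff members could handle identical participants differently.

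**Working it through.** The plan gives no figure of its own on this point, so the check sets the two rules side by side and then sizes the consequence.

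**1. The mismatch.** Assumed staging: III = 30-59, IV = 15-29, V = below 15.

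| eGFR | Entry criterion | Stopping limit |
|---|---|---|
| 75, 60 | admitted | within |
| 59, 45, 30 | admitted | already beyond |
| 29, 14 | excluded | beyond |

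The rules conflict exactly over 30-59.

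**2. What follows if such a person is enrolled.** The two readings of *develops* are alternatives and cannot both apply.
- *New onset only* (the more natural reading): a value below 60 was present at entry, so the section 7d eGFR limit cannot be triggered. For example, a fall from 45 to 31 is 14/45 = 31% and crosses no eGFR limit written there.
- *Any value below 60*: the person is removed for pre-existing kidney function. With 30 per arm, one removal is 1/30 = 3.3 percentage points. For example, the planned 10% drop-out (3/30) becomes 4/30 = 13.3%.

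**3. How many.** The documents give no eGFR distribution. Let p be the share of otherwise eligible people at 30-59, and f the share of those whom the lab review lets through. Both are assumptions. The enrolled share is q = pf / (1 - p(1 - f)), the expected number of 60 is 60q, and the chance of at least one is 1 - (1 - q)^60.

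| f | p = 1% | p = 5% | p = 10% |
|---|---|---|---|
| 0 | 0 | 0 | 0 |
| 25% | 0.15 (14%) | 0.78 (54%) | 1.62 (81%) |
| 100% | 0.6 (45%) | 3.0 (95%) | 6.0 (99.8%) |

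The range is 0 to 6 of 60. It shows only that the answer depends on p and f.

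**4. What an entry limit of 60 would not solve.** Take a true eGFR of 65, an assumed within-person CV of 5-10%, and independent normal measurements. The chance that one draw falls below 60 is L = Φ((60 - 65)/(CV × 65)), which is 6.2% at CV 5% and 22.1% at CV 10%. The chance of at least one such value at week 8 or week 16 is 1 - (1 - L)²:
- CV 5%: 1 - 0.938² = 12%
- CV 10%: 1 - 0.779² = 39%

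This applies to one person at 65 with no drug effect. It is not a trial-level rate.

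**The case against.** The strongest reply is that the safeguards already exist.

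*The drop-out route needs inconsistent behaviour.* Staff who treat any value below 60 as a reason to stop would see the screening value before the first dose, under item 2a or the three-visit option, and would not start the person. For a removal to occur, the same limit must be applied on treatment but not beforehand. This stands as a limit on likelihood: f may well be zero. It does not remove the gap in the text.

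*Other protections remain.* A reader might infer that an enrolled person at 30-59 would have no working renal safeguard at all. The documents do not support that. Section 7d also stops treatment for a possibly related adverse event of grade 3 or higher, and section 8c grades events by CTCAE version 4.0. Whether that scale sets numeric renal grades cannot be seen here. Labs at weeks 8 and 16, shift tables, physician monitoring and DSMB review also continue. What is established is narrower: on the new-onset reading, the eGFR limit in section 7d does not work for that person. Section 8a lists no renal adverse effect of TUDCA, so this is a gap in a rule and not a known hazard.

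*An entry limit is only part of the answer.* This is fair. Step 4 shows that people just above 60 can cross by chance, which only a confirmation or baseline-relative rule addresses.

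**Conclusion.** The inconsistency is real and minor. Under usual staging, the written entry criteria admit people at eGFR 30-59 who are already beyond the stopping limit, and no pre-dose review names a threshold that would keep them out.

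The effect per person is one unusable eGFR limit or 3.3 percentage points of an arm's drop-out rate, depending on the reading. The number of such people is unknown and may be zero. The 0 to 6 of 60 rests wholly on assumed p and f.

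A reader might also infer that the safety comparison is biased or the trial underpowered. Neither follows. Kidney function at entry precedes randomised treatment, so removals for it are not expected to favour an arm. The section 7c tolerability count covers only non-completion due to adverse events, so it is less exposed than the all-cause drop-out rate in section 7a. The argument for the change is that it makes two stated rules agree at almost no cost.

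**What to change.** 1. Add to section 5 an entry criterion of eGFR at or above 60 ml/min/1.73m², taken from the screening CMP already drawn.
2. Name that threshold in baseline item 2a and in the three-visit note of section 4a.
3. Optionally, state in section 7d that an on-treatment value below 60 is confirmed by repeat or judged against the participant's baseline before treatment is stopped. This handles chance crossings just above 60, which the entry limit alone does not prevent.

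The cost is a short protocol amendment touching a few places, a few more screen failures and a slightly narrower population. If p is 1-10%, as assumed above, filling 60 places needs 60/0.99 = 60.6 to 60/0.90 = 66.7 otherwise eligible people, so roughly 1 to 7 extra screened. The entry limit needs no new test, although a confirmatory repeat under item 3 would be an extra draw when triggered. The planned 30 per arm is unchanged. If staff already apply 60 before dosing, the amendment only writes that practice down.

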## 8. Risks

### a. Medical risks, listing all procedures, their major and minor risks and expected frequency.

TUDCA treatment: In previous studies of TUDCA and UDCA – adverse effects include – mainly GI related effects – diarrhea, constipation, gas, nausea, vomiting, abdominal pain and anorexia, other adverse effects which are less frequent (< 1% each) include – headache, rash and pruritus [25],[27],[30].

While no serious adverse effects have been note in previous studies, several of the described AEs could lead to issues with tolerability in MS patients especially those with bowel function abnormalities.

In a recent trial of TUDCA 1 gm twice daily in patients with Amyotrophic lateral sclerosis there were no serious adverse effects.

Venipuncture: The potential risks include discomfort, bleeding or bruising at site of blood draw, and in rare cases fainting or infection.

Clinical examination (including EDSS, MSFC): There are no significant risks of this procedure.

Stool specimen collection: There are no significant risks of this procedure.

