#### Grading of Adverse Events

We will use the National Cancer Institute's Common Terminology Criteria for Adverse Events (CTCAE) version 4.0 to report and grade all adverse events, whether or not they are related to disease progression or treatment. The relationship between an adverse event and the study drug will be determined by the site investigator and recorded on the appropriate form.

Serious Adverse Event Reporting The following process for reporting a serious adverse event will ensure compliance with the International Conference on Harmonisation guidelines:

1. The Institutional Review Board will be notified in one business day of a serious adverse event.
2. Standard reporting will occur if the event is serious, expected and drug-related, serious, expected and not drug-related, or serious, unexpected and not drug-related.
3. Expedited reporting is required if the event is serious, unexpected and drug-related. This type of event must be reported to the appropriate authorities within 15 days unless it is fatal or life-threatening; a fatal or life-threatening event must be reported within 7 days.

Pregnancy Reporting Requirements: Any pregnancy that occurs during a clinical study with an investigational drug will be reported to the IRB and DSMB, and pregnancies will be followed to their conclusion. Female participants should immediately inform the investigator of pregnancies and will stop taking the study medications. The investigator will report pregnancies to the Institutional Review Board and DSMB within one business day. The investigator will counsel the participant about the risks of continuing the pregnancy

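### Protocol-mandated treatment stops that are not classed as SAEs have no route to the DSMB before its next scheduled meeting, up to 12 weeks away in a 16-week course

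*Combined protocol and SAP*

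**What the plan says.** Section 7d works at two levels.

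- **Participant level.** Treatment stops for laboratory values ("serum AST or ALT > 3 x upper limit of normal, serum bilirubin > 3 x upper limit of normal", and an eGFR limit of 60), for intolerance, or for an event of grade 3 or higher that may be related to treatment. Pregnancy and the participant's own wish also end treatment.
- **Study level.** There are two hold triggers: "If more than 3 subjects experience serious adverse events, the study will be put on hold" and "Any death that is at least possibly related to the study will put the study on hold".

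For DSMB contact, Section 7d says "The DSMB will meet every 12 weeks and any time an SAE occurs" and "All SAEs will be reported to the DSMB delegates within 24 hours of the study staff becoming aware of the SAE". The two-business-day response also applies to SAEs. The only other between-meeting report is in Section 8c, under Grading of Adverse Events: "The investigator will report pregnancies to the Institutional Review Board and DSMB within one business day". No meeting or hold is attached to it.

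The SAE definition in Section 8c lists outcomes such as "death, a life-threatening event, inpatient hospitalization or prolongation of existing hospitalization, persistent or significant disability/ incapacity". The list contains no laboratory threshold and no CTCAE grade. Section 4f gives abnormal safety laboratory values and SAEs as separate reasons for removal. Section 7c promises real-time safety analysis but names no reviewer, threshold or action. Section 4a (Study personnel) blinds everyone except the study statistician.

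**The concern.** The primary outcome (Section 7a) is safety and tolerability, measured by adverse events and drop-out in each arm. Section 7c bases tolerability on participants who fail to complete because of adverse events. Treatment stops are therefore close to the primary signal. Section 8a points the same way: "While no serious adverse effects have been note in previous studies, several of the described AEs could lead to issues with tolerability". Yet between meetings the DSMB hears about SAEs and pregnancies, not about stops.

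An enzyme rise without symptoms, or a grade 3 gastrointestinal event managed at home, stops the participant but matches none of the listed SAE outcomes. Several such stops could accumulate while others continue to be enrolled and dosed. Site staff would see the stops but not the arms. The study statistician could see the arms but has no stated duty to escalate. The board includes a hepatologist, and no written route brings a liver-laboratory stop to that member early.

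**Working it through.** **1. The plan's own safety figure.** Section 7c claims 80% confidence that the SAE rate is below 5% if none of 30 has an SAE. Check: 1 − 0.95^30 = 0.785, which reproduces to within 2 points (the exact 80% one-sided upper limit for 0/30 is 5.2%). This figure concerns SAEs. The plan states no operating characteristics for the hold rule.

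**2. The delay.** Inputs: meetings every 12 weeks (7d), a 16-week course (4b), safety laboratory tests every 8 weeks (8b).
- Maximum wait: 12 weeks; 12/16 = 75% of the course.
- Average wait, if stops fall at random between meetings: 12/2 = 6 weeks.
- Worst case for a week-8 laboratory stop just after a meeting: 8 + 12 = week 20 on that participant's clock, 4 weeks after participants who started alongside have finished.

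**3. The hold as written.** It needs at least 4 subjects with SAEs. Across 60 participants, P(X ≥ 4) is 0.03 at a 2% SAE rate and 0.35 at 5%. Stops that are not SAEs add nothing to this count.

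**4. Stops over the whole trial.** The stop rate, and the share of stops that are also SAEs, are assumptions; neither is in the documents. X ~ Binomial(30, p) in the TUDCA arm, with no other SAEs. P(hold) uses Binomial(30, p × share).

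| Assumed stop rate | Expected stops | P(4 or more stops) | P(hold), share 0% | share 10% | share 25% |
|---|---|---|---|---|---|
| 10% | 3.0 | 0.35 | 0 | 0.0002 | 0.006 |
| 15% | 4.5 | 0.68 | 0 | 0.001 | 0.025 |
| 20% | 6.0 | 0.88 | 0 | 0.003 | 0.06 |

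At a 5% stop rate, P(4 or more stops) falls to 0.06.

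Given 6 stops, the chance that none is an SAE, and so that none prompts an unscheduled meeting, is (1 − share)^6: 1.00, 0.53 and 0.18 at shares of 0%, 10% and 25%.

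**5. Stops within one meeting interval.** The gap matters for stops that fall between two meetings. The recruitment period is not stated, so assume each stop is equally likely to fall in any of K intervals. The chance that at least one interval holds 4 or more stops is:

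| Assumed stop rate | K = 3 | K = 4 | K = 6 | K = 8 |
|---|---|---|---|---|
| 20% | 0.37 | 0.23 | 0.10 | 0.05 |
| 10% | 0.05 | 0.03 | 0.009 | 0.004 |

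**6. What if stops counted toward the hold?** With 60 participants and 5% to 10% meeting a stop criterion (assumption), P(X ≥ 4) is 0.35 to 0.86.

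**The case against.** The strongest reply is that SAE-based study holds alongside individual laboratory stops form a coherent design. Each affected participant does stop, and an independent board reviews the trial every 12 weeks. That stands: nothing here is contradictory, and the point is an improvement rather than the repair of an error.

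Several stronger readings are tempting, and the documents do not support them.

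- **That the DSMB is never told.** It is told later, at a scheduled meeting. No DSMB charter is among the documents, so any further provisions there cannot be judged.
- **That no stop could prompt an unscheduled review.** The SAE definition in Section 8c opens with a broad description, says its list may not be complete, and allows for other conditions specified in the protocol. An investigator could class some stops as SAEs, and one is enough to convene the board. This depends on individual judgement, so it narrows the gap without closing it.
- **That a large laboratory signal is expected.** Section 3 reports no safety-laboratory changes in the ALS trial at this dose over 54 weeks, and Section 8a names mainly gastrointestinal effects. A 20% laboratory-stop rate is probably high.
- **That an unseen cluster has a probability of 0.88.** That figure covers the whole trial at the highest rate tabulated. Within one interval it is 0.37 or less for 3 or more intervals.
- **That stops should simply be added to the hold count.** Section 5 excludes only stage IV/V kidney disease, while the eGFR stop in Section 7d has no baseline or relatedness condition. Some participants might enter near or below that limit, and placebo participants would count too. Step 6 shows how readily such a rule could halt the trial.

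Real-time analysis under Section 7c does not answer the point, because no person or action is attached to it.

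**Conclusion.** The point holds as a gap in notification. Between meetings, DSMB reporting depends on SAEs and pregnancy, unscheduled review depends on SAEs, and the hold depends on more than 3 subjects with SAEs or a possibly related death. A laboratory or related grade 3 stop that is not classed as an SAE waits up to 12 weeks for the board, about 6 on average.

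The structural finding rests on the text and needs no assumed rate. It does assume that at least some stops are not classed as SAEs, which fits the listed outcomes in Section 8c and the separate removal reasons in Section 4f. The probabilities rest on assumed rates and only illustrate: 0.35 to 0.88 for 4 or more TUDCA-arm stops over the whole trial at 10% to 20%, and from 0.37 down to 0.004 within any one interval over the cases shown. They do not show that such a cluster is likely.

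**What to change.** In Section 7d, require every protocol-mandated treatment stop for a laboratory threshold, or for a possibly related event of grade 3 or higher, to be reported to the DSMB on the existing 24-hour SAE route. State that the board may obtain arm assignments from the unblinded study statistician and decide whether to meet early.

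Leave the hold count and the participant-level thresholds unchanged. The sponsor and DSMB should decide whether and how stops bear on a hold. They should also reconcile the eGFR stop in Section 7d with the kidney exclusion in Section 5; this review takes no position on which should change.

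The cost is a wording amendment that uses the existing board and route, plus a few more reports and possibly some additional unscheduled reviews.
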